## Subgroups:

- Participants with and without T2DM at randomization (as-randomized strata)
- Fibrosis category (F2/F3) at randomization (as-randomized strata)

# 4.3 Pharmacokinetic Endpoint(s)

## 4.3.1 Analysis

PK results from sparse sample collection will be descriptively summarized.

## 4.3.2 Definitions and Derivations

For computing summary statistics, concentrations under the lower limit of quantification (LLOQ) will be imputed as 0 if prior to the first dose or as LLOQ/2 otherwise. Such concentrations will be displayed as '< [LLOQ]' in listings.

#### 4.3.3 Presentation

Plasma concentration will be presented by randomized arm and by visit in a summary table. The table will be based on the PK population.

# 4.4 Immunogenicity

Immunogenicity assessments will be conducted utilizing a tiered approach (screen, confirm, titer), and ADA data will be collected at scheduled visits shown in the CSP (Section 1.3.2). The ADA result from each sample will be reported as either positive or negative. ADA titer will be reported for samples confirmed positive for the presence of ADAs. Presence of ADA cross-reactive to GLP-1 and glucagon may be reported for samples confirmed positive for the presence of ADAs.

The percentage of ADA-positive patients in each category defined below will be calculated, using the number of participants in the safety analysis set by treatment group as the denominator.

- ADA positive at baseline and/or post-baseline (ADA prevalence): ADA positive at any visit, including baseline.
- TE-ADA positive (ADA incidence): The composite of both treatment-induced and treatment-boosted ADA. There is ADA incidence if either treatment induced ADA or treatment-boosted ADA is observed.
- Treatment-induced ADA positive: ADA positive post-baseline and not detected at baseline.
- Treatment-boosted ADA positive: a baseline positive ADA titer that was boosted to a 4fold or higher level (greater than the analytical variance of the assay) following drug
  administration.
- Non-TE-ADA positive: ADA positive but not fulfilling the definition of TE-ADA positive (ie, ADA positive baseline sample and at least 1 post-baseline sample ADA positive, but participant was not treatment-boosted ADA positive).
- Both baseline and post-baseline positive: ADA positive for at least 1 sample post-baseline and an ADA positive sample at baseline.
- Only baseline positive: ADA not detected for any sample post-baseline and there was an ADA positive sample at baseline.
- ADA persistently positive: defined as having at least 2 post-baseline ADA-positive measurements with at least 16 weeks (112 days) between the first and last positive measurement or at least 2 post-baseline ADA-positive measurements with an ADA-positive result at the last available assessment. The category includes participants meeting these criteria who are ADA positive at baseline.
- ADA transiently positive: defined as having at least 1 post-baseline ADA-positive measurement and not fulfilling the conditions for persistently positive. The category includes participants meeting these criteria who are ADA positive at baseline.

If ADA cross-reactivity to GLP-1 and/or glucagon is measured, the below will also be reported, using the number of participants in the safety analysis set by treatment group as the denominator.

- ADA cross-reactive to GLP-1 at baseline and/or post-baseline
- Treatment-induced ADA with cross-reactivity to GLP-1
- ADA cross-reactive to glucagon at baseline and/or post-baseline
- Treatment-induced ADA with cross-reactivity to glucagon

ADA positivity and associated titers will be reported by analysis visit. If measured, ADA with cross-reactivity to GLP-1 and/or ADA with cross-reactivity to glucagon will be summarized by visit with associated titers.

The impact of ADA on PK and association with treatment-emergent AEs (TEAEs) and treatment-emergent SAEs (TESAEs), including analysis of events with the SOC of "Immune system disorders" may be assessed, if data permits.

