# Objectives and Endpoints: Part A

Table 1 Objectives and Endpoints: Part A

Objectives	Endpoints
Primary/Safety	
To evaluate the safety and tolerability of cotadutide as compared with placebo in participants with non-cirrhotic NASH with fibrosis	Safety and tolerability will be evaluated in terms of AEs, vital signs, clinical and laboratory assessments, and ECG. Assessments related to AEs cover:  Occurrence/Frequency Relationship to IP as assessed by the investigator Intensity Seriousness Death AEs leading to discontinuation of IP AEs leading to dose reduction of IP AEs leading to dose reduction of IP AEs of special interest Adjudicated CV events including MACE, selected liver events, diabetic ketoacidosis, pancreatitis, pancreatic carcinoma, and thyroid carcinoma  Vital signs parameters include SBP, DBP, and pulse. Assessments cover: Observed value Absolute change from baseline values over time Abnormality at least once on treatment  Laboratory parameters include Clinical Chemistry (including MELD score) and Hematology parameters as well as urinalysis. A complete list of parameters is presented in Section 8.2.5. Assessments cover: Observed value Absolute change from baseline values over time Abnormality/Clinically significant abnormality in laboratory parameters at least once on treatment Treatment-emergent increase in hematuria, proteinuria, and glucose in urinalysis defined as change from negative/trace at baseline to ++, +++, or ++++ at any visit after baseline or an increase of at least ++
	Electrocardiogram measurements include heart rate, RR, PR, QRS, and QT intervals. Derived variables cover QTcF.  Assessments cover:
	
 
Observed value
 
Absolute change from baseline values over time
 

		•	ECG parameters fulfilling potentially clinically significant criteria at any time during treatment, including QRS duration > 118 ms, PR interval > 210 ms, RR < 600 ms (resting heart rate > 100 bpm), and RR > 1330 ms (resting heart rate < 45 bpm)  QTcF exceeding 450, 480, and 500 ms at any time during treatment  Change in QTcF at any time during treatment as compared to baseline exceeding 30 ms and 60 ms
•	To assess the immunogenicity of cotadutide	•	Incidence of ADAs to cotadutide and titer during treatment and follow-up
Exp	ploratory		

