# 9.4.4 Analysis of Pharmacokinetics and Immunogenicity

Immunogenicity results will be analyzed descriptively by summarizing the number and percentage of participants who develop detectable ADAs against cotadutide. The immunogenicity titer, and ADA cross-reactive to GLP-1 and glucagon will be reported for samples confirmed positive for the presence of ADAs. The effect of immunogenicity on PK and safety will be evaluated, if data allow. Sparsely collected plasma concentrations will be descriptively summarized. Any issues considered to impact the PK data (such as, but not limited to participants not receiving complete/full intended cotadutide dose) may result in the

exclusion of concentration data from the PK analysis or exclusion from the PK summaries or descriptive statistics, the reason(s) for exclusion will be documented. The available concentration data for any participants excluded from the PK data summaries or descriptive statistics will be listed. If data are used in the population PK and the exposure-response analyses, the results will be reported in a separate report.

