# 3.2 Analysis Populations

The following analysis populations are defined in Table 1:

Table 1 Populations for Analysis

Population/Analysis set	Description
Enrolled	All participants who sign the ICF.
Randomized	All participants randomized into the study.
FAS	All participants who have been randomized to and received at least 1 dose of IP.
PP	Subset of FAS population with evaluable post-baseline biopsy after at least 36 weeks of treatment. In response to a quality incident (QE-341716), participants from Site PPD will be excluded due to GCP concerns.
Safety	The Safety analysis set consists of all participants who have received at least 1 dose of IP. Erroneously treated participants (eg, those randomized to treatment A but actually given treatment B) are accounted for in the treatment group with the majority of estimated usage. In all cases, the dose level for analysis will correspond to the randomized dose.
PK	The PK population includes all participants who receive at least 1 dose of study intervention and have at least 1 complete intended PK sample containing detectable cotadutide concentrations.

FAS, full analysis set; ICF, informed consent form; IP, investigational product; PK, pharmacokinetic(s); PP, per protocol.

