#### Assessments cover:

- Observed value
- Absolute change from baseline values over time
- ECG parameters fulfilling potentially clinically significant criteria at any time during treatment, including QRS duration > 118 ms, PR interval > 210 ms, RR < 600 ms (resting heart rate > 100 bpm), and RR > 1330 ms (resting heart rate < 45 bpm)
- QTcF exceeding 450, 480, and 500 ms at any time during treatment
- Change in QTcF at any time during treatment as compared to baseline exceeding 30 ms and 60 ms

For details of the safety analysis, refer to Section 4.5.

A second primary objective is 'to assess the immunogenicity of cotadutide' with associated endpoint "incidence of ADAs to cotadutide and titer during treatment and follow-up." Details of analysis of anti-drug antibodies (ADAs) can be found in Section 4.4.

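### ADA incidence is divided by the whole safety set, so dosed participants with no post-baseline ADA result dilute a primary rate, and the handling of a missing baseline is left open.

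*SAP*

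**What the plan says.** The protocol places immunogenicity in the primary/safety block of its objectives table, with the endpoint "Incidence of ADAs to cotadutide and titer during treatment and follow-up". SAP 4.2.1 also treats it as a primary objective and refers to SAP 4.4 for the analysis.

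SAP 4.4 lists the ADA categories and gives one denominator for all of them: each percentage is taken "using the number of participants in the safety analysis set by treatment group as the denominator". The same denominator is repeated for the cross-reactivity categories, if cross-reactivity is measured. SAP 3.2 defines the set: "The Safety analysis set consists of all participants who have received at least 1 dose of IP".

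For the numerator of incidence, SAP 4.4 says: "There is ADA incidence if either treatment induced ADA or treatment-boosted ADA is observed". The induced component is defined as "Treatment-induced ADA positive: ADA positive post-baseline and not detected at baseline". The boosted component needs a positive baseline titer that later rises at least 4-fold. Persistent and transient positivity are both defined from post-baseline positive measurements.

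Protocol 9.4.4 speaks only of "summarizing the number and percentage of participants who develop detectable ADAs against cotadutide" and gives no denominator. Neither document defines an ADA-evaluable set, a rule for missing ADA samples or a not-evaluable row.

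**The concern.** The numerator and the denominator have different entry conditions. Entering the numerator for incidence requires a post-baseline result, while entering the denominator requires only a dose. A participant who is dosed and never sampled again carries no information on treatment-emergent ADA, yet reduces the percentage. The planned tables would not show how many such participants there are, so a reader could not undo the effect.

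Two definitions are also loose at the edges.

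- A participant with no baseline result and a positive later sample can be read as not detected at baseline, and so as treatment-induced, even if the antibody was already present.
- The baseline-only category, "Only baseline positive: ADA not detected for any sample post-baseline and there was an ADA positive sample at baseline", can be met by default when no later sample exists.

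At stake is the accuracy of a primary descriptive rate in arms so small that one or two participants move it visibly. No test or decision rule depends on it.

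**Working it through.** The documents state no ADA rate, so there is no planned figure to reproduce. The check is direct arithmetic.

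**Inputs from the documents**
- About 55 randomized in a 2:1:2:1 ratio (Protocol synopsis). Each cotadutide arm is 55 × 2/6 = 18.3, taken as N = 18. Both cotadutide arms together are 55 × 4/6 = 36.7, taken as 37.
- ADA serum is drawn at Weeks 0, 4, 12, 24 and 48, at the early discontinuation visit and at follow-up (Protocol Table 4).

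**Assumptions, because the documents give no value**
- m, dosed participants in an arm with no post-baseline ADA result: 0 to 4.
- p, ADA incidence among those with a post-baseline result: 20% to 80%.

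**Formula**

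Positives = p × (N − m). Reported rate = positives / N = p × (N − m)/N. The relative loss is m/N, whatever the value of p. For one participant in an arm of 18 it is 1/18 = 5.6%.

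**Reported rate for N = 18**

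| m | (N − m)/N | p = 20% | p = 40% | p = 60% | p = 80% |
|---|---|---|---|---|---|
| 0 | 1.000 | 20.0% | 40.0% | 60.0% | 80.0% |
| 1 | 0.944 | 18.9% | 37.8% | 56.7% | 75.6% |
| 2 | 0.889 | 17.8% | 35.6% | 53.3% | 71.1% |
| 3 | 0.833 | 16.7% | 33.3% | 50.0% | 66.7% |
| 4 | 0.778 | 15.6% | 31.1% | 46.7% | 62.2% |

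For m = 1 to 4 the shortfall is 1.1 to 4.4 points at p = 20% and 3.3 to 13.3 points at p = 60%. With both cotadutide arms together (N = 37) and p = 60%, it is 1.6 to 6.5 points.

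**In whole participants.** Nine treatment-emergent positives in an arm of 18 are reported as 9/18 = 50.0%. Among those with a post-baseline result, the rate is 9/17 = 52.9% if m = 1, 9/16 = 56.3% if m = 2, and 9/15 = 60.0% if m = 3.

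**Missing baseline.** This works the other way. Each participant with no baseline result whose antibody was in fact already present, and who is counted as induced, adds 1/18 = 5.6 percentage points to the reported rate in an arm of 18. The number of such participants is also unknown.

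**The case against.** The strongest reply is that m is likely to be very small. Protocol 7.1 encourages participants who stop treatment to attend the remaining visits. PK sampling is among the procedures dropped for them; ADA sampling is not. Someone who leaves before Week 4 is still due a sample at the early discontinuation visit and another at follow-up. To have no post-baseline result, a participant must miss all of these, which means early loss to follow-up or refusal of further visits. This stands, and it limits the expected size.

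It can also be said that the denominator is explicit, matches the adverse event tables, and feeds a descriptive summary with no formal testing. Positivity and titers are reported by visit as well. The shift is small beside sampling error: an exact 95% interval for 9/18 runs from about 26% to 74%. All of this is fair. It makes the point modest, but it does not make the safety set the better denominator.

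Three stronger readings are tempting, and the documents do not support them.

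- A reader might infer that the error is always downward. That is true of the denominator rule alone; the missing-baseline ambiguity can raise the induced rate.
- A reader might infer that unsampled participants are classed as ADA negative. SAP 4.4 assigns positive or negative to samples and defines no negative participant category. These participants are simply not counted as positive.
- A reader might infer that gastrointestinal drop-out makes the understatement worse on active drug. Participants who discontinue are due further samples, and dosing before the Week 4 sample is at 50 µg, the starting dose. Uneven loss is possible but not shown.

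**Conclusion.** The point holds in a limited form. Dosed participants without a post-baseline ADA result lower the reported treatment-emergent, persistent and transient rates by the factor (N − m)/N, and nothing else in the documents corrects this. In an arm of about 18 the relative loss is about 5.6% per such participant. The absolute size depends on m and on the true rate, neither of which the documents give; the ranges above are assumptions. The sampling schedule makes a small m likely, and at m = 0 the effect disappears. Prevalence is less exposed, because a baseline sample alone can satisfy it. The classification of a missing baseline is a separate gap that can push incidence up. The net direction in the final table therefore cannot be stated in advance.

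**What to change.** In SAP 4.4, replace the single denominator as follows:

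- **Incidence, treatment-induced, persistent and transient ADA, and the matching cross-reactivity categories:** safety-set participants with at least one post-baseline ADA result.
- **Treatment-boosted ADA:** the same, and a baseline result as well.
- **Prevalence:** safety-set participants with at least one ADA result at any time.

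Show the evaluable number per arm beside each percentage, and keep the safety-set percentage as a supporting figure.

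State how a participant with a missing baseline and a positive later sample is classified. One option is to exclude such participants from the induced category. The other is to count them, in line with the missing-baseline convention in SAP 4.5 for laboratory, vital sign and ECG abnormalities. Excluding them drops observed positives; counting them may include antibodies already present. Either is workable if the number is shown. Also say whether the baseline-only category requires a later sample to exist.

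The cost is a short SAP edit, one extra dataset flag and a slightly smaller denominator. No new data are needed, and if every dosed participant has a post-baseline result, the incidence, induced, persistent and transient percentages do not change through the denominator.

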Urine for albumin and creatinine	X			X			X			X	X	
HbA1c (Section 8.1.5)	X			X			X			X	X	
Fasting serum lipid panel (Section 8.1.5)	X									X	X	
Pre-dose blood for PK analysis (Section 8.4)	X	X		X			X			X	X	X
Serum for immunogenicity (ADA) (Section 8.4.2)	X	X		X			X			X	X	X
Blood sampling for ELF (Section 8.1.5)	X									X	X	

Table 4 Schedule of Activities for Part A: Treatment Period and Follow-up

				ŗ	Freatmen	nent Period						
Week	0	4	8	12	16	20	24	32	40	48		Follow-up
Visit	V2	V3	V4	V5	V6	V7	V8	V9	V10	V11 (EOT)	Visit b 4 weeks after EO	4 weeks after EOT or E/D (± 5d) a
Day	1	29	57	85	113	141	169	225	281	337		
(visit window $\pm x$ days) a	1	± 5d	± 5d	± 5d	± 5d	± 5d	± 5d	± 5d	± 5d	± 5d		
Blood sampling for Pro-C3 (Section 8.1.5)	X									X	X	
FIB-4 computed score (Section 8.1.5)	X									X	X	
Blood for fasting plasma glucose-(Section 8.1.5)	X									X	X	
Blood for C-peptide (Section 8.1.5)	X									X	X	
Blood for adiponectin (Section 8.1.5)	X									X	X	
Genomics Initiative optional, exploratory genetic sample (Section 8.6, Appendix D) °	X											
Optional biomarker serum sample (for biomarker research) (Section 8.5.2)	X									X	X	

Participants should withhold alcohol and refrain from intense exercise for 24 hours prior to each study site visit.

- Visit windows should be calculated from Day 1. Visit 2 (randomization) may be scheduled any day following confirmation that participant meets all eligibility criteria including eligibility reading from the central pathology review of the biopsy (historical or on-study) sample and laboratory report assessments from the central laboratory (eg, the screening period does not need to be a full 8 weeks). Follow-up visit conducted 4 weeks (± 5 d) after EOT visit or E/D visit. For participants who discontinue study intervention permanently and do not continue with study visits, follow-up visit should be performed 4 weeks (± 5 d) after the E/D visit. For participants who discontinue study intervention early but continue with study visits, follow-up visit should be performed 4 weeks (± 5 d) after the EOT.
- b Performed in event of early discontinuation of study intervention or withdrawal from study.
- c Activities related to demonstration and training on SC administration can be conducted at Visit 1 and/or prior to randomization at Visit 2.

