#### 1 INTRODUCTION

The purpose of this document is to give details for the statistical analysis of study D5671C00006 Part A data supporting the clinical study report (CSR). The reader is referred to the clinical study protocol (CSP) and the case report form (CRF) for details of study conduct and data collection.

This study was originally designed as a 2-part, Phase IIb/III, global, randomized, parallel-group, double-blind, placebo-controlled, multicenter study to assess the safety and efficacy of 300 and 600 µg cotadutide compared with placebo, given once daily as a subcutaneous injection administered via a multidose pen, in adults with non-cirrhotic non-alcoholic steatohepatitis (NASH) with fibrosis stage F2 or F3. After carefully considering several factors, foremost being the identification of other, more convenient treatments for patients with NASH, the sponsor made a strategic decision to discontinue development of cotadutide and recruitment into this study. Randomized participants and participants in active screening were allowed to continue participation. Given the reduced sample size, the primary goal of this study is to evaluate the safety and tolerability of cotadutide in participants with non-cirrhotic NASH with fibrosis. The originally planned Phase III portion of the study (Part B) will not be conducted and most references to it have been removed from this document.

Part A (Phase II) will assess the safety and efficacy of 300 μg and 600 μg cotadutide treatment.

In Part A, 300 participants were originally planned to be randomized to provide > 90% power for the test of each dose versus pooled placebo to detect a difference of 20% in NASH resolution assuming a placebo response rate of 15%. As a result of the decision to terminate recruitment, approximately 55 participants are planned to be randomized in the study.

At randomization, participants in Part A will be stratified by the presence/absence of type 2 diabetes mellitus (T2DM) and by fibrosis stage.

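### SAP 4.4 reports a participant whose only post-baseline ADA-positive result is the last available sample as transiently positive, although no later negative shows that the antibody was lost

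*SAP*

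**What the plan says.** SAP 4.4 gives two routes to persistently positive. The first is "at least 2 post-baseline ADA-positive measurements with at least 16 weeks (112 days) between the first and last positive measurement". The second is "at least 2 post-baseline ADA-positive measurements with an ADA-positive result at the last available assessment". Transiently positive is the residual class, "having at least 1 post-baseline ADA-positive measurement and not fulfilling the conditions for persistently positive". The SAP states that both classes include participants who were already positive at baseline. There is no indeterminate class. Percentages are calculated "using the number of participants in the safety analysis set by treatment group as the denominator".

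Protocol Table 4 (section 1.3.2.1) schedules post-baseline ADA serum at Weeks 4, 12, 24 and 48, at the early discontinuation (E/D) visit and at follow-up. On the timing of the last of these it says: "Follow-up visit conducted 4 weeks (± 5 d) after EOT visit or E/D visit". No ADA sample is planned after that.

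Immunogenicity is a primary objective. Its endpoint, restated in SAP 4.2.1, is "incidence of ADAs to cotadutide and titer during treatment and follow-up".

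**The concern.** A reader takes transient to mean that the antibody appeared and then went away. The SAP definition does not require that. It gives the label to anyone who fails the persistence test, including a participant whose series ends on a first positive. For that participant the duration of the response was not observed, and the schedule has no later sample that could settle it.

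The second route to persistence shows that the SAP already treats a series ending on a positive as a special case: two positives only about four weeks apart, at Week 48 and follow-up, count as persistent. With one positive fewer, the same open-ended series gets the opposite label and is not called unknown. The baseline-positive case is sharper. Someone positive at baseline and at the only post-baseline sample has been positive at every sample taken, yet is reported as transient.

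At stake is the meaning of one row in a primary-objective table, the row a reader would use to judge whether antibody responses resolve.

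**Working it through.** **The plan's own figure.** 16 weeks × 7 = 112 days, as SAP 4.4 states.

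**Inputs.** The two persistent routes and the residual definition come from SAP 4.4. The sample days are 29, 85, 169 and 337 (SAP Table 7 target days for Weeks 4, 12, 24 and 48), plus 365 for follow-up (337 + 28). About 55 participants are randomized (SAP section 1) in a 2:1:2:1 ratio (Protocol 6.3.1).

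**Step 1: apply the rule to every pattern for a completer.** Five samples give 2^5 − 1 = 31 patterns with at least one positive. Of these, 24 are persistent and 7 are transient. The seven transient patterns are:

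- a single positive at Week 4, 12, 24 or 48, followed by a negative (4 patterns);
- positives at Weeks 4 and 12 only (85 − 29 = 56 days), ending negative;
- positives at Weeks 12 and 24 only (169 − 85 = 84 days), ending negative;
- a single positive at follow-up, with nothing after it.

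Six of the seven end on a negative. One does not.

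**Step 2: shorter series, for participants with fewer samples.**

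| Post-baseline samples | Persistent | Transient | Transient with sole positive last |
|---|---|---|---|
| 5 | 24 | 7 | 1 |
| 4 | 9 | 6 | 1 |
| 3 | 3 | 4 | 1 |
| 2 | 1 | 2 | 1 |
| 1 | 0 | 1 | 1 |

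A participant with one post-baseline sample can never be persistent. If that sample is positive, the label is always transient. These are counts of patterns, not probabilities.

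**Step 3: the disputed cases form one clean group.** Any series with two or more positives that ends positive is persistent by the second route. A series that is not persistent but ends positive must therefore have exactly one positive, the last. Requiring a negative last assessment for transient removes exactly this group and no other. For completers the split goes from 24 / 7 to 24 persistent / 6 transient / 1 indeterminate.

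**Step 4: size.** 55 × 2/6 = 18.3 per cotadutide arm, assuming that all randomized participants are dosed and so enter the safety set. One participant is 1/18.3 = 5.5 percentage points. For an assumed 0, 1, 2 or 3 such participants in an arm, the transient percentage falls by 0, 5.5, 10.9 or 16.4 points. The documents give nothing from which to choose among these.

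**Step 5: would another output show it?** SAP 4.4 reports ADA by analysis visit, but SAP Table 7 has no follow-up row. Its Week 48 window runs from Day 254 to Day 378, and SAP 3.3.2 keeps the record closest to Day 337. For a completer with an on-schedule Week 48 sample, a follow-up sample near Day 365 falls in that window and is not selected. The by-visit table would then not show a follow-up-only positive.

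**The case against.** Several points on the other side stand.

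- **Persistence was not shown either.** The two-positive minimum is an explicit choice, and the persistent row leaves out only people in whom persistence was not demonstrated. A reader might infer that persistence is understated. The documents do not support that: one positive at the last sample shows neither persistence nor loss. It would be an understatement only if some of these participants would have stayed positive, which cannot be known.
- **The definition does not lean one way overall.** Positives at Week 48 and follow-up only, 365 − 337 = 28 days apart, count as persistent. So do positives at Weeks 4 and 24 (169 − 29 = 140 days) followed by negatives at Week 48 and follow-up, where the antibody was lost. A reader might infer a rule built to reassure; the definition as a whole does not show that.
- **The named endpoint is incidence and titer.** Protocol 9.4.4 does not mention the persistent/transient split, which is an added SAP descriptor.
- **Early leavers are mostly covered.** Table 4 takes ADA at the E/D visit and again at follow-up. Protocol 7.1 encourages participants who stop drug to remain for later procedures, and its exceptions name PK sampling but not ADA. The early-leaver problem is therefore largely confined to those who miss these samples.
- **Context.** The analysis is descriptive, the trial is small, development has stopped, and the SAP amendment history says the ADA definitions were aligned with standard tables. Individual results will appear in listings (SAP 3.3.3).

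These points limit the reach and importance of the issue. They do not justify a label that implies resolution where none was observed, and a listing does not correct a percentage in a summary table.

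**Conclusion.** The point holds in a limited form. As written, SAP 4.4 labels a sole positive at the last available sample as transient. The transient percentage thus mixes resolved with unresolved responses, and the persistent percentage is a lower bound with respect to the unresolved ones. ADA prevalence, treatment-emergent incidence and titer do not depend on the split, so the primary immunogenicity endpoint is unchanged.

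The effect is about 5.5 points on the transient percentage per affected participant in an arm of about 18. How many will be affected is unknown and may be zero. A reader might try to estimate a share of converters from the schedule, but the answer depends wholly on the assumption. Equal chances of first detection at each of five samples would put 1/5 = 20% at follow-up; even onset over time would put 28/364 = 7.7% there. The documents support neither.

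This is an inexpensive improvement to the reporting of a primary objective and does not threaten the trial's conclusions.

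**What to change.** In SAP 4.4, define transiently positive as at least one post-baseline positive, not meeting the persistent definition, and a negative result at the last available assessment. Add a row for indeterminate, covering participants whose sole post-baseline positive is the last available sample, whatever their baseline status. Leave the persistent definition unchanged. By step 3 of the working, the three rows then account for every participant with a post-baseline positive, with no overlap.

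The cost is one sentence and one table row, with a small programming change and no new samples. The downside is a category that may hold very few participants or none, and a departure from the standard table layout.
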